12.7.1.1 Overall Adverse Event Summary

An overall adverse event summary will provide, by treatment arm, the number and percentage of patients with at least:

- One TEAE,
- One TEAE related to IMP,
- One confirmed or suspected COVID-19 TEAE (as defined in [Section 10.21.2](#)),
- One TEAE leading to permanent IMP discontinuation,
- One TEAE related to IMP leading to permanent IMP discontinuation,
- One serious TEAE,
- One serious TEAE related to IMP,
- One TEAE with outcome of death,
- One AE with outcome of death related to IMP,
- One TEAE of special interest.

This table will also present the number of TEAEs and the number of TEAE of special interest by treatment arm.

12.7.1.2 All-causality Treatment-emergent Adverse Event Summary

Descriptive presentations of TEAEs will be given by PT and SOC for the Safety Analysis Set. The number and percentage of patients reporting at least one TEAE within a given treatment arm will be provided as described below

- *All TEAEs by SOC and PT,
- *All TEAEs by SOC, PT and subgroups (as described in [Table 12.7-1](#)),
- Most common TEAEs (incidence $\geq 5\%$ in either treatment arm) by SOC and PT,
- Most common TEAEs (incidence $\geq 2\%$ patients in either treatment arm) by SOC and PT,
- Most common TEAEs (incidence $\geq 2\%$ patients in either treatment arm) by SOC, and PT and subgroups (as described in [Table 12.7-1](#)),
- All TEAEs by SOC, PT and maximum severity,
- All TEAEs by SOC, PT and worst action taken on study drug,
- All TEAEs by SOC, PT and time of first onset of AE categorized as:
1-7 day, 8 to 14 days, 15 to 21 days and > 21 days (as described in [Section 10.21.3](#)),
- All TEAEs by SOC, PT and AE duration, categorized as:
1-7 day, 8 to 14 days, 15 to 28 days, 29 to 42 days ,43 to 61 days , > 61 days, ongoing, indeterminate (as described in [Section 10.21.4](#)),
- All TEAEs by SOC, PT and relationship to IMP,
- All treatment-related TEAEs by SOC and PT and maximum severity,
- *All treatment-related TEAEs by SOC and PT and subgroups (as described in [Table 12.7-1](#)),

- *All treatment-related TEAEs leading to permanent IMP discontinuation by SOC and PT,
- *All TEAEs leading to permanent IMP discontinuation by SOC and PT,
- *All TEAEs leading to permanent IMP discontinuation by SOC and PT and subgroups (as described in [Table 12.7-1](#)),
- All treatment-related TEAEs leading to permanent IMP discontinuation by SOC and PT and maximum severity,
- All non-serious TEAEs by SOC and PT,
- All most common non-serious TEAEs (incidence $\geq 5\%$ in either treatment arm) by SOC and PT.

**These tables will also present the total number of AEs by treatment arm and as appropriate by category of subgroup.*

12.7.2 Death, Serious Adverse Events and Other Significant Adverse Events

12.7.2.1 Death

All deaths recorded in the EDC as adverse events, as the result of an adverse event or as fatal outcome of an adverse event will be listed and summarized as described in [Section 12.7.1](#) and described in depth as narrative.

Descriptive presentations of fatal TEAEs will be given by PT and SOC for the Safety Analysis Set. The number and percentage of patients reporting at least one fatal TEAE within a given treatment arm will be provided as described below:

- All TEAEs leading to death by SOC and PT (if at least 1 patient experienced a fatal issue TEAE),
- All treatment-related TEAEs leading to death by SOC and PT (if at least 2 patients experienced a fatal issue TEAE related to study drug).

These tables will also present the total number of AEs by treatment arm.

12.7.2.2 Serious Adverse Events

Descriptive presentations of serious TEAEs will be given by PT and SOC for the Safety Analysis Set. The number and percentage of patients reporting at least one serious TEAE within a given treatment arm will be provided as described below:

- All serious TEAEs by SOC and PT,
- All serious TEAEs by SOC, PT and subgroups (as described [Table 12.7-1](#)),
- All serious TEAEs leading to permanent IMP discontinuation by SOC and PT,
- All serious treatment-related TEAEs by SOC and PT,
- All serious treatment-related TEAEs by SOC and PT leading to permanent IMP discontinuation by SOC and PT,

These tables will also present the total number of AEs by treatment arm and as appropriate by category of subgroup.

12.7.2.3 Adverse Events of Special Interest

An adverse events of special interest (AESI) is any adverse event of scientific or medical interest to the study medication. The types of AESIs which will be analyzed are presented in **Descriptive presentations of AESIs** will be given for each AESI category on the safety analysis set presenting:

- The number and percentage of patients with at least one treatment-emergent AESI,
- The number and percentage of patients with at least one treatment-emergent AESI by SOC and PT,
- The number and percentage of patients with at least one severe treatment-emergent AESI,

- The number and percentage of patient with at least one serious treatment-emergent AESI,
- The number of and percentage of patients with at least one treatment-emergent AESI leading to permanent IMP discontinuation,
- The number of treatment-emergent AESI,
- The number of severe treatment-emergent AESI,
- The number of serious treatment-emergent AESI,
- The number of treatment-emergent AESI leading to permanent IMP discontinuation,
- The number of unique* treatment-emergent AESI,
- The number of unique* severe treatment-emergent AESI,
- The number of unique* serious treatment-emergent AESI,
- The number of unique* treatment-emergent AESI leading to permanent IMP discontinuation,
- The time to first onset of treatment-emergent AESI categorized as :1-7 day, 8 to 14 days, 15 to 21 days, 21 to 28 days and > 28 days (as described in [Section 10.21.3](#)),

**Unique AESI is defined as any AESI coded with the same PT and having the same date of onset.*

Analysis of time to first onset of AESIs will be conducted by actual treatment arm on the Safety Analysis SAS using the SAS® LIFEEST procedure.

Assuming no carry over effect, Kaplan-Meier plots (estimates) of cumulative incidence of first onset of AESI will be provided by actual treatment arm on the Safety analysis set. The time to AESI onset (in days) is defined as the number of days from 1st IMP intake of the treatment arm (e.g., nabiximols, placebo) the AESI is emergent to (as defined in [Section 12.7.1](#)) until the onset of the AESI (see detailed in [Section 10.21.4](#)).

For patients not known to have experienced an AESI during respectively Period 1 and Period 2:

- Period 1 censoring day is the date of 1st IMP intake during Period 2 minus 1 day for those patients continuing in Period 2 and, the end of study date for those patients who discontinued before Period 2,
- Period 2 censoring day is the end of study date in the period.

Additionally, for lost to follow-up patients:

- Period 1 censoring day is the earliest date between end of study date in the period and the planned Visit 6 day minus 1 day (Day 30),
- Period 2 censoring day is the earliest date between end of study date in the period and the planned Visit 10 day (Day 58).

To accompany the Kaplan-Meier (KM) plots, summary tables will display the KM estimates of cumulative probabilities (with 95% CI calculated based on the Greenwood method when applicable).

- of patients with an event at a specific time point such as 7, 14, 21, 28 (if applicable) days after 1st IMP intake in the studied period;
- time to first event based on the 10th, 20th, 30th, 40th, 50th (median) and 75th percentiles.

If the estimate of lower bound of the 95% CI is below '0' or the estimate of the upper bound of the 95% CI is over '1', then it will be respectively restricted to '0' and '1'.

The number of patients at risk along with the number and percentage of patients censored and with an event, using the number of patients at risk as denominator to calculate the percentage will also be displayed.

Each Kaplan-Meier plot (estimates) will only be provided if more than 5 patients are presenting an event in each treatment arm.

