6.0 Introduction

This SAP addendum should be read in conjunction with the study protocol V1.0 dated 22Jul2020, CRF V1.0 04Jul2021 and SAP V1.0 08Jun2022.

Final approval of the SAP addendum will occur prior to study unblinding.

The decision was made on 9th November 2022 to discontinue the study and halt any further enrollment of patients without the planned number of patients being recruited. As a result of this, an abbreviation of the planned analysis and reporting as detailed in the protocol and SAP will be conducted.

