7.0 Statistical Methods

The abbreviated reporting will follow the strategy as detailed in **Table 3.2-1**.

Table 3.2-1 Strategy for abbreviated reporting

Hierarchy	GWSP20105	
Primary	LLMT-6	Inferential and descriptive statistics; no supplementary, no subgroup analyses and no imputations for missing data
Secondary	LLMT-4	As established in study SAP to support safety assessment of Nabiximols as a globally marketed product
	TEAEs	
	Vital signs	
	Labs	
	ECG	
	C-SSRS	
Exploratory	PK	No processing, analyses, or reporting
	T25FW	Data cleaning for inclusion in listings; no descriptive or inferential statistics
	NRS spasticity	
	Daily spasm count	
	MSSS-88	

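### The AESI Kaplan-Meier output requires more than 5 patients with an event in each arm, so it drops out for an event that is frequent on nabiximols and rare on placebo

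*SAP*

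**What the plan says.** SAP 12.7.2.3 states that "Kaplan-Meier plots (estimates) of cumulative incidence of first onset of AESI will be provided by actual treatment arm on the Safety analysis set". It adds that "To accompany the Kaplan-Meier (KM) plots, summary tables will display the KM estimates of cumulative probabilities", with Greenwood 95% intervals cut off at 0 and 1, at days 7, 14, 21 and (if applicable) 28, together with time percentiles from the 10th to the 75th. Numbers at risk, censored and with an event are also to be shown. The section closes with the condition at issue: "Each Kaplan-Meier plot (estimates) will only be provided if more than 5 patients are presenting an event in each treatment arm". There is no exception for imbalance and no one-arm fallback.

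The same section lists other AESI output with no such condition. It begins with "The number and percentage of patients with at least one treatment-emergent AESI" and goes on to severe and serious events, events leading to permanent discontinuation, and categorized onset times. SAP 12.7.1 lists AESIs by patient.

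The SAP addendum records the decision to "halt any further enrollment of patients without the planned number of patients being recruited". Its Table 3.2-1 keeps the safety reporting "As established in study SAP to support safety assessment of Nabiximols as a globally marketed product". It does not revisit the threshold.

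**The concern.** A minimum event count makes sense where sparse data would destabilise a comparison. Here nothing is compared formally: 12.7.2.3 has no log-rank test, hazard ratio or model, and each curve is estimated from its own arm. Requiring events in both arms therefore lets the placebo count decide whether the nabiximols estimates appear. The wording is symmetric, but an AESI caused by the drug would tend to have many events on nabiximols and few on placebo, and that is the pattern for which the rule withholds the time course. AESIs with similar rates in both arms would keep theirs.

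The threshold is also an absolute count. It becomes harder to meet as the trial gets smaller, and enrolment was stopped short of plan.

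**Working it through.** **Inputs.**
- Rule: at least 6 patients with an event in each arm (SAP 12.7.2.3).
- Planned size: about 190 randomized and at least 170 completing both periods (SAP 8.2). In a crossover each arm has nearly all patients, so 180 per arm is used as a midpoint.
- Size after the halt: not given. 60 and 85 per arm are assumptions.
- AESI rates: not given. All rates below are assumptions.

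The plan states no figure for this rule, so there is none to reproduce.

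**Step 1: what the rule does to fixed counts, 180 per arm** (Fisher exact p, arms treated as independent).

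| Nabiximols | Placebo | Fisher p | Output shown? |
|---|---|---|---|
| 30 | 5 | 0.000009 | No |
| 18 | 4 | 0.0033 | No |
| 7 | 7 | 1.0 | Yes |

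**Step 2: the placebo incidence needed.** 6/180 = 3.3%; 6/60 = 10%.

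**Step 3: chance that the output appears.** With X binomial in each arm:
- current rule: P(shown) = P(X_nab ≥ 6) × P(X_plc ≥ 6)
- either-arm rule: P(shown) = 1 − P(X_nab ≤ 5) × P(X_plc ≤ 5)

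| Per arm | Nabiximols | Placebo | P(X_nab ≥ 6) | P(X_plc ≥ 6) | Current rule | Either-arm rule |
|---|---|---|---|---|---|---|
| 180 | 10% | 1% | 0.9998 | 0.010 | 1% | >99.9% |
| 180 | 10% | 2% | 0.9998 | 0.154 | 15% | >99.9% |
| 180 | 10% | 3% | 0.9998 | 0.455 | 45% | >99.9% |
| 180 | 20% | 5% | 1.000 | 0.891 | 89% | 100% |
| 85 | 20% | 5% | 0.9998 | 0.252 | 25% | >99.9% |
| 60 | 20% | 5% | 0.988 | 0.079 | 8% | 99% |

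The same patients contribute to both arms, so independence is only approximate, but it hardly matters. Whatever the dependence, P(both) lies between P(X_plc ≥ 6) − [1 − P(X_nab ≥ 6)] and P(X_plc ≥ 6). At 180 per arm that is within 0.0002 of the placebo column. At 60 per arm it runs from 0.079 − 0.012 = 0.067 to 0.079. The placebo arm drives the result.

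**Step 4: would plain Greenwood limits serve in a sparse arm?** With no censoring, the Kaplan-Meier cumulative incidence is F = x/N, its Greenwood standard error is √(F(1−F)/N), and the limits are F ± 1.96 SE, cut off at 0.

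| Events / N | Greenwood 95% | Exact 95% |
|---|---|---|
| 0/60 | 0 to 0% | 0 to 6.0% |
| 1/60 | 0 to 4.9% | 0.04 to 8.9% |
| 2/180 | 0 to 2.6% | 0.1 to 4.0% |

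The upper limit is too low in each case. Loosening the trigger without changing the interval would overstate certainty about the placebo arm.

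**The case against.** Four points on the other side carry weight.

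- **No safety signal is hidden.** A reader might infer that the rule conceals a nabiximols excess. The documents do not support that: the AESI counts, percentages, severity, onset categories and listings are all unconditional.
- **Kaplan-Meier may add little by Day 21.** Patients who continue are censored the day before their first Period 2 dose, around Day 30, and the plan allows for about 20 withdrawals among 190. Only early leavers are censored before Day 21, so the crude percentage should usually be close to the Kaplan-Meier estimate. It would also be too strong to say that the remaining onset tables ignore censoring. SAP 12.7.1 gives interval-specific at-risk denominators for onset tables by system organ class (SOC) and preferred term (PT), although its general definition of at risk is having taken at least one spray, and the AESI onset table states no denominator.
- **A per-group minimum is the SAP's own habit.** SAP 12.1 has the same condition for discontinuation plots by sequence, and 12.5.2.3.2 drops the responder model if either arm has fewer than 5 responders. The common-TEAE tables in 12.7.1.2 do use a threshold "in either treatment arm) by SOC and PT", but that selects terms for listing and does not decide whether an estimate is produced. A reader might infer that the AESI rule breaks with SAP convention; it does not.
- **A minimum has a rationale.** Step 4 shows that Greenwood limits perform badly with few events, and most of the planned percentiles could not be estimated in such an arm.

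These points limit the importance of the finding and shape the fix. They do not explain why the nabiximols curve should depend on placebo events. The model in 12.5.2.3.2 needs responders in both arms; a within-arm curve does not. The interval problem can be solved by choosing a different interval for the sparse arm.

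**Conclusion.** The point stands as a low-cost improvement to the reporting. When an AESI is frequent on nabiximols and rare on placebo, the planned time-course output is dropped. What goes is the curve, the cumulative probabilities with intervals, and the percentiles. That the accompanying tables go with the plot is the natural reading, since the condition covers plot and estimates together, but the wording could be clearer.

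Under assumed rates of 10% against 1% to 3% with 180 per arm, the output appears 1% to 45% of the time. At an assumed 60 per arm with 20% against 5%, it appears about 8% of the time. The size depends wholly on the assumed rates: at 180 per arm and 20% against 5%, it would be shown 89% of the time. Whether the Kaplan-Meier output survives the early termination is also an inference, because the addendum keeps treatment-emergent adverse event (TEAE) reporting but does not name AESIs separately.

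**What to change.** In the last sentence of SAP 12.7.2.3, change *each* treatment arm to *either* treatment arm, and say that the accompanying tables follow the same rule. Once triggered, show both arms with the numbers at risk, censored and with an event that are already planned.

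For an arm with 5 or fewer events, replace the plain Greenwood limits with log-log limits, or with exact binomial limits if it has no events. Print percentiles that cannot be estimated as not estimable.

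If the analysis is already fixed, these can be supplied as additional outputs and described in the study report, where Protocol 13 already requires departures from the SAP to be set out.

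The cost is a short text change and a few more figures and tables. Estimates in the sparse arm will be imprecise, and the revised limits will show it.

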12.7.3 Laboratory Data

The clinical safety laboratory data (hematology and biochemistry) are planned to be collected at Screening and Day 21 of each treatment period. In case of premature end of treatment the latest assessment collected on-treatment will be used as described in [Table 10.1-1](#).

For the purposes of summarization in both the tables and listings, all laboratory values will be converted to standardized units. The investigator and medical monitor will be provided with a list of the normal ranges used by the central clinical laboratory for all variables assayed during the trial and a statement of accreditation (or similar) for the laboratory. However, AST, ALT, GGT, ALP and total bilirubin will be summarized using SI units.

Only scheduled laboratory parameters defined in [Appendix 2](#) and those derived from them as eGFR (as defined in [Section 10.13](#)) will be included in summary tables and figures. However unscheduled laboratories values (coming from central or local laboratories) will be used in abnormality summary tables and will be presented in listings (using categories as defined in [Appendix 6 Abnormality Criteria](#)).

Baseline (Screening), Day 21 of each treatment period and the change from baseline to Day 21 (end of the treatment) will be summarized using the safety analysis set, by treatment arm, separately for red blood cells parameters and white blood cells parameters, hepatobiliary parameters, renal parameters, coagulation parameters and electrolytes and proteins (as described in [Appendix 2](#)). Furthermore, AST, ALT, GGT, ALP and total bilirubin will also be summarized as a multiple of the upper limit of normal (ULN).

Laboratory hematology and biochemistry (as described in [Appendix 2 Clinical laboratory parameters](#)) abnormalities will be evaluated, on patients from the Safety Analysis Set using shift tables at Day 21 according to baseline status with categories based on:

- reference ranges as either normal, below the lower limit of normal (LLN) as “Low” or above the ULN as “High”,
- based on CTCAE toxicity grade using version 5.0 or higher (as defined in [Appendix 4 Toxicity Criteria for Laboratory Hematology and coagulation Parameters](#) based on CTCAE version 5.0 for hematology parameters and in [Appendix 5 Toxicity Criteria for Laboratory Biochemistry Parameters](#) based on CTCAE version 5.0 for biochemistry parameters),

presented by treatment arm.

Shift tables based on reference ranges will also be repeated for the subgroups presented in [Table 12.7-1](#).

Furthermore, a summary of patients with laboratory values outside the reference ranges at baseline and during each 21-day on-treatment safety period (as defined in [Section 10.1.1](#)) will be presented for scheduled parameter including either scheduled visit only or scheduled and unscheduled visits, by treatment arm.

Scatterplot presenting baseline against last on-treatment value within each treatment period will be presented by treatment arm for scheduled biochemistry and hematological parameters of interest.

Regarding AST, ALT, GGT, ALP and total bilirubin these parameters will be summarized by treatment arm within the Safety Analysis Set for Day 21 of each treatment period using SI units and as a proportion of the population with no missing assessment if abnormal values with reference to ULN are presented using the All laboratory values will be listed and all test values outside the normal range will be flagged.

Urinalysis results will be summarized and listed.

12.7.3.1 Potential Drug-induced Liver Injury (DILI)

Liver function test data will also be provided in separate listings for:

- Patients who possibly met Hy's Law criteria (i.e., had any elevated ALT or AST of $> 3 \times$ ULN, and increase in total bilirubin $\geq 2 \times$ ULN, at the same visit)
- Patients who met any one or more of the following criteria at any post-baseline visit (list laboratory parameters ALT, AST, and total bilirubin only)
- ALT or AST $> 3 \times$ ULN with the appearance of fatigue, nausea, vomiting, right upper quadrant pain or tenderness, fever, rash, and/or eosinophilia ($> 5\%$)
- ALT or AST $> 8 \times$ ULN
- ALT or AST $> 5 \times$ ULN for more than 2 weeks
- ALT or AST $> 3 \times$ ULN and (TBL $> 2 \times$ ULN or INR > 1.5)

A summary table will also be provided by treatment arm for number of patients who met any of the criteria specified above at any post-baseline visit. Any elevation during the wash-out period will be linked to the actual treatment arm received during Period 1 whereas any elevation observed permanent treatment discontinuation will be linked to the last treatment received.

A drug-induced serious hepatotoxicity (DISH) plot will display, for each patient during each 21-day on-treatment safety period (as defined in [Section 10.1.1](#)) the maximal total bilirubin value (expressed as a multiple of the ULN) against the maximal ALT value (expressed multiple of the ULN) to identify possible Hy's Law range or Temple's Corollary.

All post-baseline potential drug-induced liver injury laboratory data will be listed.

12.7.4 Vital Signs

Vital signs will include sitting SBP and DBP and pulse rate which are planned to be measured at Day 1 H0, Day 1 H3, Day 15 and Day 21 of each treatment period as well as during the screening and the FU visit.

Vital signs parameters will be summarized on the Safety Analysis Set as described below.

Observed and change from baseline value in vital signs measures at each scheduled timepoint (Day 1 H3, Day 15, Day 21) will be summarized by treatment arm.

The number and percentage of patients with any clinically significant abnormal value and change in vital signs (as defined in [Appendix 6 Abnormality Criteria](#)**Error! Reference source not found.**) within each treatment period will be summarized by treatment arm within the Safety Analysis Set.

Observed and change from baseline (Screening) to FU will also be summarized by treatment sequence.

All vital signs data will be listed.

12.7.5 Physical Examination, ECGs and other Observation Related to Safety

12.7.5.1 Physical Examination: Weight and BMI

Weight is planned to be measured at Screening, Day 1 H0 of each period and at follow-up visit.

Based on the Safety Analysis Set, weight and BMI (as defined in [Section 10.11](#)), observed and change from baseline value at each scheduled timepoint (Period 2 Day 1 H0, Day 21) will be summarized by treatment arm.

Observed and change from Screening to FU will also be summarized by treatment sequence.

The number and percentage of patients meeting a clinically significant change in weight (as defined in [Appendix 6 Abnormality Criteria](#) at any time during within each treatment period will be summarized by treatment arm. All measurements (scheduled or unscheduled) will be used to determine if any abnormality criteria is met (as determined in [Appendix 6 Abnormality Criteria](#)).

Weight and BMI will be listed.

